[figure not shown]

**Study information**

Title	Comparative Analysis of Outcomes among Patients Initiating Xeljanz in Combination with Oral MTX Who Withdraw MTX Versus Continue MTX Using a United States Healthcare Claims Database
Protocol number	A3921336
Protocol version identifier	Version 1
Date of last version of protocol	01 May 2018
Active substance	L04AA29 (tofacitinib)
Medicinal product	Xeljanz (tofacitinib)
Research question and objectives	
Primary Objective:
 
Compare treatment patterns including dosing, concomitant medication use, adherence, persistence, and switching among tofacitinb+MTX patients who withdraw MTX vs. persist with MTX or experience interrupted MTX.
 
Secondary Objectives:
 
Explore the differences in demographic and clinical characteristics among tofacitinb+MTX patients who withdraw MTX vs. persist with MTX or experience interrupted MTX.
 
Compare rheumatoid arthritis (RA)-related costs among tofacitinb+MTX patients who withdraw MTX vs. persist with MTX or experience interrupted MTX.
 
Compare medication effectiveness among tofacitinb+MTX patients who withdraw MTX vs. persist with MTX or experience interrupted MTX.
 
Compare all-cause and RA-related health care utilization among tofacitinb+MTX patients who withdraw MTX vs. persist with MTX or experience interrupted MTX.
 
Compare all-cause healthcare costs among tofacitinb+MTX patients who withdraw MTX vs. persist with MTX or experience interrupted MTX.

Author(s)	PPD [REDACTED] PPD [REDACTED], Ph.D
------------------	--

## 1. LIST OF ABBREVIATIONS

Abbreviation	Definition
AE	Adverse Event
AHRQ	Agency for Healthcare Research and Quality
ARRA	American Recovery and Reinvestment Act
CIRAS	Claims-based index for RA severity
CMS	Centers for Medicare & Medicaid Services
COB	Coordination of benefits
COPD	Chronic obstructive pulmonary disease
CPI	Consumer price index
CPT	Current Procedural Terminology
ED	Emergency department
ER	Emergency room
FDA	Food and Drug Administration
GLM	Generalized linear model
HCFA	Care Financing Administration
HCPCS	Healthcare Common Procedure Coding System
HIPAA	Health Insurance Portability and Accountability Act
ICD-9 CM	The International Classification of Diseases, 9th Revision, Clinical Modification
IEC	Independent Ethics Committee
IRB	Institutional review board
ISPOR	International society for pharmacoeconomics and outcomes research
IV	Intravenous
MTX	Methotrexate
NB-DMARD	Non-biologic disease modifying antirheumatic drug
NDC	National Drug Code
NIS	Non-interventional study
NSAID	Non steroidal anti-inflammatory drug
PDC	Proportion of Days Covered
RA	Rheumatoid Arthritis
RAPID3	Routine assessment of patient index data
RX	Outpatient pharmacy
TNFi	Tumor-Necrosis Factor-alpha inhibitor
UB	Uniform Bill
US	United States

## 3. ABSTRACT

Not applicable.

## 4. AMENDMENTS AND UPDATES

None.

## 5. MILESTONES

Milestone	Planned date
Start of data collection	1 May 2018
End of data collection	31 May 2018
Final study report	30 September 2018

## 6. RATIONALE AND BACKGROUND

Tofacitinib was approved by the Food and Drug Administration (FDA) in November 2012 for the treatment of adult patients with moderately to severely active rheumatoid arthritis who have had an inadequate response or intolerance to methotrexate. It may be used as monotherapy or in combination with methotrexate (MTX) or other nonbiologic disease-modifying antirheumatic drugs (NB-DMARDs).

Pfizer is currently conducting a phase 3b/4 study (A3921192) which was designed to evaluate the sustained efficacy and safety of tofacitinib modified release formulation (11 mg QD) after withdrawal of MTX versus tofacitinib modified release formulation plus continued MTX treatment in subjects with moderate to severe rheumatoid arthritis who are insufficiently responding to their stable dose of methotrexate treatment. This retrospective claims analysis is designed to compare the effectiveness and treatment patterns among tofacitinib+MTX patients who withdraw MTX vs. continue MTX in a real world setting.

## 7. RESEARCH OBJECTIVES

The primary and secondary objectives will be conducted among patients who are identified from the Truven Health MarketScan Research Database.

### Primary Objective

- Compare treatment patterns including dosing, concomitant medication use, adherence, persistence, and switching among tofacitinib+MTX patients who withdraw MTX vs. persist with MTX or experience interrupted MTX.

### Secondary Objectives

1. Explore the differences in demographic and clinical characteristics among tofacitinib+MTX patients who withdraw MTX vs. persist with MTX or experience interrupted MTX.
2. To compare RA-related costs among tofacitinib+MTX patients who withdraw MTX vs. persist with MTX or experience interrupted MTX.
3. Compare medication effectiveness among tofacitinib+MTX patients who withdraw MTX vs. persist with MTX or experience interrupted MTX.
4. Compare all-cause and RA-related health care utilization among tofacitinib+MTX patients who withdraw MTX vs. persist with MTX or experience interrupted MTX.
5. Compare all-cause healthcare costs among tofacitinib+MTX patients who withdraw MTX vs. persist with MTX or experience interrupted MTX.

## 8. RESEARCH METHODS

### 8.1. Study Design

To address the objectives, a retrospective cohort design will be employed to evaluate patient characteristics, treatment patterns, medication effectiveness, and health care cost and utilization in RA patients newly initiating tofacitinib in combination with oral MTX between January of 2014 and January 2017 utilizing the Truven Health MarketScan Research Database, see [Section 8.7](#) below.

### 8.2. Setting

This study will utilize the de-identified claims data in the Truven Health MarketScan Research Database.

### 8.2.1. Inclusion Criteria

This study will include individuals who are privately insured and with Medicare Supplemental insurance paid for by their employers and initiating tofacitinib in combination with MTX for RA between 01 January 2014 and 31 January 2017. To be included in the final study sample, patients must meet the following inclusion criteria:

1. At least one claim for tofacitinib between 01 January 2014 and 31 January 2017 (the identification period).

- a. **Medication index date.** The index date will be the date of the first claim for tofacitinib during the identification period.

*Note: Patients will have a variable length baseline of at least a year long. The baseline period will be censored at January 1, 2012 based on licensed data availability. The majority of baseline measures will use data from the 12 months immediately prior to the index date. Select measures will use data during the entire variable length baseline.*

- b. Tofacitinib initiation. Patients must have a 2nd claim for tofacitinib within 60 days of the end of the days supplied from their index claim (at least two claims with no 60 day gap).
- c. Oral MTX initiation. Patients must have an initial prescription for oral MTX in the period between 30 days prior to index date and 30 days following index date followed by a 2nd prescription for oral MTX within 60 days of the end of the days supplied from their initial MTX claim (at least two claims/administrations with no 60 day gap).

2. Presence of The International Classification of Diseases, 9th Revision, Clinical Modification (ICD-9 CM) code for RA (in any position) during the one-year pre-index period or on the index date. ICD-9 = 714.0x-714.4x & 714.81 or ICD10 = M05.\* & M06.0\*-M06.3\* or M06.8\*-M06.9\*.

3. At least 18 years old as of the index date.

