### 8.6.3. Treatment Patterns

- **Non-persistence.** A 0/1 flag will be created to identify if the patient is not persistent with tofacitinib before the end of the 12 month follow-up period.

Non-persistence will be identified based on a gap in treatment with the index medication or switching to another biologic.

Among patients with 1 year of follow-up, persistence through the end of the 1 year follow-up will be identified. Persistence will be identified based on the day supply (or presumed day supply) and fill dates of claims for the index medication (see [Table 2](#) for a listing of presumed day supplies). Persistence with the index medication will be defined as not having a gap in therapy of at least 60 days between fills/infusions. For retail pharmacy (RX) claims the day supply will be utilized. For Healthcare Common Procedure Coding System (HCPCS) claims a presumed day supply derived from the product label will be utilized. A gap of at least 60 days between the run-out date (service date + day supply-1) and the next service date will be considered non-persistence. Patients with early refills will be allowed to accumulate a stockpile of the index medication of up to 14 days for later use.

- **Post persistence treatment patterns.** Patients who are not persistent for the entire follow-up period will be classified into the following mutually exclusive categories based on the first occurrence of non-persistence: switch immediately, discontinue then restart, discontinue then switch, discontinue and never switch or restart.
  - **Switch immediately.** Patients will be classified as switching immediately if they initiate a non-index biologic before a 60-day gap in treatment is observed for the index medication.
  - **Discontinue then restart.** Patients will be classified as discontinuing and then restarting if there is a gap in the index therapy of at least 60 days and the first medication observed after the gap is the index medication.
  - **Discontinue then switch.** Patients will be classified as discontinuing and then switching if there is a gap in the index therapy of at least 60 days and the first medication observed after the gap is a biologic (including Tofacitinib) different from index medication.

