## Secondary Objectives

- **Explore the differences in demographic and clinical characteristics among tofacitinb+MTX patients who discontinue MTX vs. persist with MTX or experience interrupted MTX.**

For this objective descriptive analysis will be conducted. The goal of this objective will be to describe the respective populations and explore the presence of demographic differences between the cohorts. Known demographic characteristics (eg, age, gender geographic location, pre-index cost and utilization) will be summarized. In addition, other patient characteristics (eg, most common comorbid diagnoses and most common medications received) will be summarized.

- **To compare RA-related costs among tofacitinb+MTX patients who discontinue MTX vs. persist with MTX or experience interrupted MTX.**

For this objective both descriptive and multivariable analysis will be conducted. For the descriptive analysis, 12-month RA-related cost measures will be presented per patient during the baseline and follow-up periods. The change in health care cost from baseline to follow-up will be identified. In addition, total RA-related health care cost will be presented in each of the months of the baseline and follow-up. The mean cost in each month will be included on a figure demonstrating the trend in costs over time. Multivariable analysis of cost will also be conducted using generalized linear models (see [Section 8.10.3](#)).

- **Compare medication effectiveness using a validated claims-based algorithm among tofacitinb+MTX patients who discontinue MTX vs. persist with MTX or experience interrupted MTX.**

Medication effectiveness at one year will be examined by the medication cohorts of interest using patients who have at least 1 year of follow-up. For this objective both descriptive analysis and multivariable analysis will be used. Descriptive analysis will focus on quantifying the percentage of patients who are effectively treated at one year. Analysis of this objective may also include multivariable analysis (eg, logistic regression). Specifically, the dependent variable will be effectively treated at one year (yes/no) and the independent variables will be study cohort, demographic characteristics, characteristics of interest, and other characteristics identified from previous objectives (see [Section 8.10.4](#)).

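### Criterion 1b removes patients whose first tofacitinib gap already meets the 60-day non-persistence rule, although persistence, switching and effectiveness are counted from the first fill

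*Combined protocol and SAP*

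**What the plan says.** Section 8.2.1 sets time zero: "The index date will be the date of the first claim for tofacitinib during the identification period". Criterion 1b, under the label of tofacitinib initiation, then requires a second "claim for tofacitinib within 60 days of the end of the days supplied from their index claim", summarised in parentheses as "at least two claims with no 60 day gap". Section 8.5 reads outcomes over the twelve months after the index date and requires at least 24 months of continuous enrolment.

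Section 8.6.3 flags "if the patient is not persistent with tofacitinib before the end of the 12 month follow-up period". It adds: "Non-persistence will be identified based on a gap in treatment with the index medication or switching to another biologic". The gap limb is specified as "A gap of at least 60 days between the run-out date (service date + day supply-1) and the next service date". A patient is an immediate switcher if "they initiate a non-index biologic before a 60-day gap in treatment is observed for the index medication".

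Persistence and switching belong to the primary objective (Section 7). Effectiveness is a secondary objective. Section 8.6.4 makes a patient a failure on any one of six criteria, including adherence to the index drug and absence of a switch. Section 8.10 says the descriptive analysis will focus on "quantifying the percentage of patients who are effectively treated at one year".

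The limitations in Section 8.12 do not mention the two-claim requirement, and no analysis of all first-fill patients is planned.

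**The concern.** Entry depends on something that happens after the index date, inside the outcome window, and that event is the first opportunity to fail a primary-objective outcome. A patient who fills once and never returns is non-persistent by Section 8.6.3, but never reaches the analysis. The patient is not lost to follow-up, because the enrolment requirement means the missing refill is visible in the claims.

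What is at stake is how the results read. Section 8.1 describes patients newly starting tofacitinib with oral MTX, and follow-up runs from the index date. A reader will take the persistence and effectiveness percentages as applying from that date, when the earliest failures have been taken out. If those failures are unevenly spread over the MTX cohorts, the comparison between cohorts is affected as well.

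**Working it through.** The plan states no persistence figure, one-fill share or sample size, so there is no figure to reproduce. The check has four parts.

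**1. Do the two rules coincide?** Put the index fill on day 0 with S days' supply, so run-out is day S − 1 (Section 8.6.3). A next fill on day d satisfies 1b if d − (S − 1) ≤ 60 and counts as non-persistence if d − (S − 1) ≥ 60.

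| S | Last day allowed by 1b | First non-persistent day |
|---|---|---|
| 30 | 29 + 60 = 89 | 89 |
| 60 | 59 + 60 = 119 | 119 |
| 90 | 89 + 60 = 149 | 149 |

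The rules are complementary except on the boundary day, where the parenthesis in 1b points to exclusion. The match is by rule and not exact in operation: Section 8.6.3 allows a 14-day stockpile and Table 2 rounds day supply to 30-day periods, while 1b mentions neither. Some patients could be classified differently by a few days.

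**2. Which patients does 1b remove?**
- One fill only: removed.
- Restart after a first gap of 60 days or more: removed.
- Switch with no second tofacitinib claim in the window: removed.
- Switch, but with a second tofacitinib claim in the window: kept and counted as a switcher, because 1b has no switch limb.

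**3. Effect on levels.** Let f be the one-fill share among patients who otherwise qualify. All of them are non-persistent, so

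persistence from first fill = reported persistence × (1 − f).

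With an assumed reported value of 60%:
- f = 5%: 0.60 × 0.95 = 0.57
- f = 10%: 0.60 × 0.90 = 0.54
- f = 20%: 0.60 × 0.80 = 0.48

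The overstatement is 3 to 12 points. Late restarters are non-persistent too, so for persistence they add to f.

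For effectiveness the factor does not carry over to everyone removed. One-fill patients have a proportion of days covered of 30/365 = 0.082, 60/365 = 0.164 or 90/365 = 0.247. Section 8.6.4 asks for high adherence without giving a cut-off; against the 0.8 that Section 8.6.3 uses for the medication possession ratio, they fail clearly. Patients who switched fail the no-switch criterion. A late restarter could reach (365 − 60)/365 = 0.836 and so need not fail.

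**4. Effect on the MTX contrast.** Reported persistence = p/(1 − f), where p is persistence from first fill. Take p = 0.50 in both cohorts:
- f = 10% in both: 0.556 and 0.556, difference 0.
- f = 10% and 20%: 0.50/0.90 = 0.556 and 0.50/0.80 = 0.625, a spurious 6.9 points.
- f = 5% and 25%: 0.50/0.95 = 0.526 and 0.50/0.75 = 0.667, a spurious 14.0 points.

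With equal f of 10% but p of 0.50 and 0.60, the reported values are 0.556 and 0.667: the 10-point difference is stretched to 11.1 points. All of these inputs are illustrations.

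**The case against.** The best defence is that 1b is the plan's open definition of initiation. Criterion 1c applies the same idea to MTX, cohorts are assigned after combination therapy has begun, and the research question is MTX withdrawal against continuation. Someone with a single claim may never have taken the drug. On this view the results are right for the population as defined, and the inclusion criterion itself states the condition.

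This stands as a reason to keep 1b in the main analysis. It does not remove the problem, because a two-claim definition of initiation fits a clock that starts at the second claim, and this plan starts it at the first. The limitations do not disclose the consequence.

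A second objection also has force. With a 30-day index fill, tofacitinib runs out on day 29, whereas an MTX gap of more than 60 days that begins on or after the index date cannot be complete before about day 60. Some one-fill patients would be placed in an MTX cohort by a gap completed after their tofacitinib supply ended. Adding them to the cohort comparison mixes in cases where the classifying event follows the outcome. This limits what an analysis without 1b can show about the contrast.

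The primary objective is also a comparison of cohorts, and the 57% to 48% figures concern only the overall level. That is correct.

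**Conclusion.** The concern holds for levels. As written, persistence from first fill is overstated, and early discontinuation, late restart, and switching without a second fill go uncounted. Effectiveness is overstated to the extent that the removed patients would fail it. The 3 to 12 points rest on an assumed reported persistence of 60% and an assumed one-fill share of 5% to 20%; the documents give neither.

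A reader might infer more, in four ways that the documents do not support:
- That 1b is the whole non-persistence rule in advance. It mirrors the gap limb only, and switchers who refill in time are retained.
- That the effectiveness percentage shrinks by the same factor. This needs every removed patient to fail, and late restarters may not.
- That the overall switching percentage is too low. That depends on whether removed patients switch more often than those kept, which is not stated.
- That the MTX comparison is biased in a known direction. It is distorted only if the removed share or persistence from first fill differs by cohort, and nothing in the documents gives size or sign.

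The point deserves a change to the plan, but it does not invalidate the design.

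**What to change.** Keep 1b in the main analysis and make three additions.

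1. In the attrition table, give the number removed by 1b alone, by MTX cohort. If it is small in every cohort, the matter is closed.
2. Label the main results as applying to patients with at least two tofacitinib fills, and add the restriction to Section 8.12.
3. Add a sensitivity analysis of tofacitinib persistence, switching and effectiveness without 1b, all other criteria unchanged. Count one-fill patients as non-persistent and not effectively treated. Classify late restarters and switchers by the plan's own rules in Sections 8.6.3 and 8.6.4. Costs and utilization can stay on the main set.

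The cost is one further analysis set from claims already held. State two downsides with the results: some one-fill patients may never have taken the drug, and the MTX cohort of some may be fixed by a gap completed after their tofacitinib supply ended. The sensitivity analysis is therefore informative mainly about overall levels, and its cohort contrast should be read with caution.

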### 8.3. Cohort Assignment

Patients will be assigned to a study cohort based on MTX status following initiation of combination therapy with tofacitinib and MTX. The “MTX discontinued” cohort will contain patients who experience a gap in MTX therapy of >60 days within 12 months post-index. The “MTX interrupted” cohort will contain patients who experience a gap in MTX therapy of >60 days with 1 or more subsequent fills within 12 months post-index. The “MTX persistent” cohort will contain patients with no gap >60 days within 12 months post-index. If sample size is insufficient, the MTX “discontinued” and “MTX interrupted” cohorts may be combined.

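### Criterion 1c requires neither an MTX claim on or after the tofacitinib index date nor any shared supply, so some patients with only pre-index MTX fills enter as combination users who discontinued MTX

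*Combined protocol and SAP*

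**What the plan says.** Section 8.1 describes the population as "RA patients newly initiating tofacitinib in combination with oral MTX between January of 2014 and January 2017". The lead-in to 8.2.1 says the same: "initiating tofacitinib in combination with MTX for RA". The operational rules are these:

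- **Index date (8.2.1, 1a):** "The index date will be the date of the first claim for tofacitinib during the identification period".
- **Tofacitinib (1b):** a second "claim for tofacitinib within 60 days of the end of the days supplied from their index claim". MTX is not mentioned.
- **MTX (1c), first fill:** "initial prescription for oral MTX in the period between 30 days prior to index date and 30 days following index date".
- **MTX (1c), second fill:** "followed by a 2 nd prescription for oral MTX within 60 days of the end of the days supplied from their initial MTX claim".
- **Cohorts (8.3):** "Patients will be assigned to a study cohort based on MTX status following initiation of combination therapy with tofacitinib and MTX". Under that rule, the MTX-discontinued cohort holds "patients who experience a gap in MTX therapy of >60 days within 12 months post-index". Those who later refill form the interrupted cohort.

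The exclusions in 8.2.2 do not remove patients whose last MTX fill precedes index. Section 8.4 plans a subset treated with MTX before index, so prior MTX users are eligible. Section 8.10 points to 8.10.2 for monotherapy versus combination regimens, but 8.10.2 defines neither.

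**The concern.** The study asks what follows when patients on tofacitinib plus MTX stop MTX. Section 8.3 takes it as given that combination therapy was started, but 1b and 1c do not guarantee it. The MTX count may begin and end before index, and nothing ties the second MTX fill to tofacitinib.

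A patient with two pre-index MTX fills and none later meets every stated criterion, although the claims show no MTX dispensed once tofacitinib began. Without a refill there is bound to be a gap of more than 60 days, so such patients can only enter the MTX-discontinued cohort, the one that defines the research question.

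A measure under the primary objective also fails for them. The MTX adherence measure in 8.6.3 counts its denominator from the first MTX claim in follow-up, and these patients have no such claim. Section 8.10.6 expects a fairly small sample, so a modest number of misplaced patients could matter.

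**Working it through.** The plan gives no figure to reproduce: 8.8 states that no sample size was computed. The check applies the written rules to possible fill dates.

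**Inputs.** Day 0 is the first tofacitinib claim (1a). The first MTX fill lies between day -30 and day +30, and the second is due within 60 days of the first fill's run-out (1c). Run-out = service date + days supplied - 1 (8.6.3, stated for tofacitinib and assumed here for MTX). MTX days supplied are not given, so 7, 14, 28, 30, 84 and 90 days were tried. A 14-day MTX stockpile is also assumed, because 8.6.3 allows one only for the index drug.

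**Step 1: can both MTX fills precede index?** Yes. Days -30 to -1 contain 30 × 29 / 2 = 435 pairs of fill dates. All 435 satisfy 1c for every days supply tried.

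**Step 2: where does 8.3 put these patients if they never refill?** In the MTX-discontinued cohort, for all 435 pairs and every days supply.
- 30-day fills on days -30 and -1: with one day carried over, supply ends on day 29, and the gap exceeds 60 days on day 29 + 61 = 90.
- The longest case tried, 90-day fills, leaves at most 103 days of supply from index (last covered day 102). The gap exceeds 60 days on day 102 + 61 = 163, still within 12 months.

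**Step 3: can MTX supply end before tofacitinib begins?** Yes. With 14-day fills on days -30 and -16, the second run-out is -16 + 14 - 1 = -3.

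**Step 4: can overlap be zero when MTX is filled after index?** Yes, with alternating fills.
- 30-day MTX fills on days -30 and +30 cover -30 to -1 and 30 to 59.
- 30-day tofacitinib fills on days 0 and 60 cover 0 to 29 and 60 to 89.
- Each refill comes 31 days after run-out, well inside the limit, and no day is shared.

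These patients do fill MTX after index. Their cohort depends on later fills and could be any of the three.

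**Step 5: how often would Step 1 arise?** Take a patient who refills every L days and stops MTX at index, with every refill phase equally likely (an assumption). The last pre-index fill is on one of days -L to -1, and the fill before it must be no earlier than day -30. Hence share = max(0, min(L, 30 - L)) / L.

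| Refill interval L | Both fills before index |
|---|---|
| 14 days | 14/14 = 100% |
| 25 days | 5/25 = 20% |
| 28 days | 2/28 = 7% |
| 30 days | 0/30 = 0% |
| 90 days | 0/90 = 0% |

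**The case against.** **The wording already means combination users.** The phrase appears in 8.1 and 8.2.1 but is never made operational. Section 8.11 says analyses are programmed to the protocol's specifications, so 1b and 1c decide who enters. Nor does the word initiation in 1c limit entry to new MTX starters, given the subset in 8.4. Even a new starter can fill twice within 30 days before index.

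**A pre-index fill does not prove that MTX was replaced.** This stands. With 28-day fills on days -30 and -2, supply runs to day 25, so the two drugs overlap on paper for 26 days (days 0 to 25). That patient may have swapped drugs at index or may be a genuine, very early withdrawer. With 30-day fills both before index, leftover supply covers 1 to 29 days from index without a stockpile and 15 to 43 days with one. Claims cannot tell leftover supply from use. Only where supply ends before day 0 do the claims show no possible combined use from these fills.

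**Criterion 1c already screens out many patients who stop MTX at index.** This also stands. On the Step 5 assumptions it removes all regular 30-day and 90-day refillers and 26 of 28 (93%) at 28 days. A reader might infer that patients who replaced MTX with tofacitinib enter as a group. Only those with this fill pattern do.

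**Conclusion.** The gap in the rule is real. As written, 1b and 1c admit patients with no MTX claim on or after index, and in some of them MTX supply has ended before tofacitinib starts. Section 8.3 labels them as having discontinued MTX after combination therapy, and their MTX adherence is undefined.

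The number affected cannot be found from the documents. It depends on MTX days supply and refill timing. The range of 0% to 100% above applies only to regular refillers who stop MTX at index; it is not a share of the cohort.

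A reader might go further and put a share on the cohort. With S the proportion who stop MTX at index, f the Step 5 share and w the later withdrawal rate in the rest, that share is S·f / (S·f + (1 - S)·w).
- S = 0.20, f = 2/28, w = 0.35 gives 0.0143 / 0.2943 = 4.9%.
- S = 0.40, f = 0.20, w = 0.25 gives 0.08 / 0.23 = 35%.
- At 30-day intervals f = 0, so the share is 0%.

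The documents give neither S nor w, so these values only show how far the answer moves with the assumptions.

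A reader might also infer a one-sided bias in every objective. One-way assignment holds only when both fills precede index and no refill follows. Alternating-fill patients can land in any cohort, and nothing in the documents fixes a direction of bias for any outcome.

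**What to change.** Add to 1c that at least one oral MTX claim must fall on or after the index date, and that MTX and tofacitinib days supplied must overlap after index. The sponsor should choose and justify any minimum overlap before outcomes are analysed. A fixed 30 days, for example, would drop a patient given 28 days of each drug on day 0 who then stops MTX, which is an early withdrawal the study wants to observe. The claim requirement matters most, because leftover supply can create overlap on paper.

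Keep the tofacitinib index date as the start of follow-up. Moving it to the first day of overlap would conflict with the 12-month outcome period that 8.5 runs from index. Report how many patients the rule removes, by cohort, and repeat the main comparisons under 1c as it now stands as a sensitivity analysis.

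The cost is a line of text and a check on data already held. The withdrawal cohort becomes somewhat smaller, and some genuine very early withdrawers are lost. Because patients with no MTX claim after index all sit in the MTX-discontinued cohort, the claim requirement removes patients from that cohort alone. The count and the sensitivity analysis should therefore be reported with the main result.
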